6.13. Withdrawal Consent

Patients who request to discontinue receipt of study treatment will remain in the study and must continue to be followed for protocol-specified follow-up procedures. The only exception to this is when a patient specifically withdraws consent for any further contact with him or her or persons previously authorized by the patient to provide this information. Patients should notify the investigator in writing of the decision to withdraw consent from future follow-up, whenever possible. The withdrawal of consent should be explained in detail in the medical records by the investigator, as to whether the withdrawal is only from further receipt of study treatment or also from study procedures and/or posttreatment study follow-up and entered on the appropriate CRF page. In the event that vital status (whether the patient is alive or dead) is being measured, publicly available information should be used to determine vital status only as appropriately directed in accordance with local law.

7. STUDY ASSESSMENTS AND PROCEDURES

Study procedures and their timing are summarized in the SoA (Table 3). Protocol waivers or exemptions are not allowed. Safety concerns should be discussed with the Sponsor Medical Monitor immediately upon occurrence or awareness to determine if the patient should continue or discontinue study treatment. Adherence to the study design requirements, including those specified in the SoA, is essential and required for study conduct.

7.1. Screening Procedures

Screening is the interval between signing the ICF and the day the patient is enrolled in the study (Cycle 1 Day 1). Screening may not exceed 28 days. Assessments that are required to demonstrate eligibility may be performed over the course of 1 or more days during the screening process.

Procedures conducted as part of the patient's routine clinical management (e.g., blood count, imaging study) and obtained before signing of the ICF may be used for screening or baseline purposes provided the procedures met the protocol-specified criteria and were performed within the time frame defined in the SoA (Table 3). If baseline scans from an institution other than the investigational site are used, the site must obtain copies of the radiographic scans prior to enrollment of the patient, or the scans must be repeated at the investigational site and submitted.

All screening evaluations must be completed and reviewed to confirm that potential patients meet all eligibility criteria. The Investigator will maintain a screening log to record details of all patients screened and to confirm eligibility or record reasons for screening failure, as applicable. Tests with results that fail eligibility requirements may be repeated once during screening if the Investigator believes the results to be in error. For screening assessments that are repeated, the most recent available results before enrollment will be used to determine eligibility.

See Section 5.4 and Section 6.11 for information regarding screen failures and replacement of patients, respectively.

7.1.1. Baseline Documentation of Intracranial Target and non-Target Lesions

All baseline lesion assessments must be performed 28 days prior to the first dose of study treatment. Refer to [Appendix 5](#).

Note:

- Cystic lesions thought to represent cystic metastases should not be selected as target lesions when other suitable target lesions are available.
- **Measurable intracranial lesions that have been previously irradiated and have not been shown to be progressing following irradiation should not be considered as target lesions.**
- Prior excision of a single melanoma brain metastasis is allowed and may be selected as a target lesion provided there is regrowth in the cavity.

All other intracranial lesions should be identified as non-target and should also be recorded at baseline. Measurements of non-target lesions are not required, but the presence or absence of each should be noted throughout follow-up.

7.1.2. Baseline Documentation of Extracranial Target and non-Target Lesions

All baseline lesion assessments must be performed 28 days prior to the first dose of study treatment. Refer to [Appendix 4](#).

Note: Measurable extracranial lesions that have been previously irradiated and have not been shown to be progressing following irradiation should not be considered as target lesions.

All other lesions (or sites of disease, excluding the brain) should be identified as non-target and should also be recorded at baseline. Non-target lesions will be grouped by organ. Measurements of these lesions are not required, but the presence or absence of each should be noted throughout follow-up.

7.2. Efficacy Assessments

All data acquired for efficacy purposes (e.g., CT, MRI, X-ray, FDG-PET, pathology reports, caliper measurements and measurements of tumor markers) obtained at Screening and while on study, including off-schedule imaging studies, will be made available if requested by the Sponsor.

7.2.1. Radiological Tumor Evaluation

Appropriate radiological scans of all suspected sites of disease are performed until disease progression using the same method and technique throughout the study. Target lesions should demonstrate the patient's baseline tumor burden and should be selected based on their size (i.e., lesions with the longest diameter) and their suitability for accurate repeat assessment. See the SoA ([Table 3](#)) for the schedule of brain and extracranial assessments.

When possible, each center will have a designated radiologist responsible for the interpretation of scans and response evaluations for study patients. A single radiologist should perform all evaluations for an individual patient.

Assessments will be performed until disease progression, withdrawal of consent, initiation of subsequent anticancer therapy, patient is lost to follow up, death or defined end of study (Section 4.4).

The following will be performed:

- Screening and on treatment gadolinium-enhanced MRI of the brain.
- Screening and on treatment chest, abdomen and pelvis CT (or MRI) scans.
- An MRI of spine is required at screening only.
- Skeletal lesions identified at baseline will continue to be imaged at subsequent scheduled visits using localized CT, MRI or X-ray (using the same method used at baseline for all visits for any given lesion). After baseline, whole-body bone scans need not be repeated unless clinically indicated.
- Additional imaging evaluations may be performed at any time if there is symptomatic evidence suggesting the possibility of disease progression based on clinical symptoms or physical examination.

If off-schedule imaging evaluations are performed or if progression is suspected, every effort should be made to perform subsequent imaging evaluations in accordance with the original imaging schedule.

Extracranial lesions will be assessed using RECIST v1.1 (Eisenhauer et al, 2009, Appendix 4); brain metastasis will be assessed per mRECIST v1.1 (Appendix 5) and per RANO-BM in an exploratory analysis (Lin et al, 2015). All CT scans will be performed with IV contrast. If a patient is known to have a medical contraindication to the contrast agent or develops a contraindication during the study, a CT scan without IV contrast of the chest and MRI with IV contrast, if possible, of the abdomen and pelvis may be performed. Chest X-ray or ultrasound will not be used for tumor response assessments in this study.

Any extracranial lesions that have been subjected to loco-regional therapies (e.g., radiotherapy, ablation, etc.) will not be considered measurable unless they have clearly progressed since the therapy. Previously treated lesions that have not progressed will be considered non-measurable and assessed as non-target lesions.

While FDG-PET scans are not required for this study, sites may perform extracranial imaging by PET-CT provided the CT is of similar diagnostic quality as CT performed without PET, including the use of oral and IV contrast media. If acquired according to local standards, FDG-PET may be used to document PD in accordance with RECIST v1.1.

The initial Screening imaging should be performed within 28 days of the first dose of study treatment. Post-Screening assessments will be performed as described in the SoA (Table 3) (± 7 days). **Imaging will not be delayed for delays in cycle start.** Every effort must be made to assess each lesion that is measured at Screening by the same method throughout the study to enable consistent comparison.

Confirmation of brain, extracranial and global CR and PR is required. Confirmation assessments must be performed no less than 4 weeks after the criteria for response have initially been met and may be performed at the next scheduled assessment. If a confirmation assessment is performed prior to the next scheduled assessment, the next scheduled evaluation is still required (i.e., regularly scheduled study visit evaluations must occur at each scheduled time point regardless of unscheduled assessments). Partial response can be confirmed at an assessment later than the next assessment after the initial documentation of PR. If the criteria for a CR or PR are not confirmed, then SD can be considered the best response if it has been demonstrated for a minimum of 6 weeks.

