1.3. Schedule of Activities (SoA)

Table 3. Schedule of Activities

Procedure/Assessment (± 3-day window for all Treatment Period visits except for C1D1 [no window])	Screening	Treatment Period					Post-treatment Period			Notes/Protocol Section
		Cycle 1		Cycle 2	Subsequent Cycles		EOT	30-Day Follow up	Surviva l Follow up	
Evaluation/Window	Day -28 to -1	Day 1	Day 15	Day 1	Day 1	Day 15	± 7D	± 7D	Q12W ± 7D	
Informed consent	X									See Sections 7.1 and 9.4
Inclusion/exclusion criteria	X	X								See Section 5.1 and 5.2
Demography and baseline characteristics	X									See Section 7.3.1
Tumor sample (archival or fresh biopsy)	X									Central laboratory testing to confirm BRAFV600 status. See Section 7.2.6 and Section 7.9
Tumor sample (optional)							X			See Section 7.9.1
CCI [REDACTED]	■			■	■		■			[REDACTED]
[REDACTED]	■			■	+		■			[REDACTED]
Medical history, cancer diagnosis, extent of cancer (including AJCC stage)	X									See Section 7.3.2
Prior systemic cancer therapies, radiation and surgeries	X									See Section 7.3.2
Contact IWRS	X	X		X	X		X			See Section 6.3

Table 3. Schedule of Activities

Procedure/Assessment (± 3-day window for all Treatment Period visits except for C1D1 [no window])	Screening	Treatment Period					Post-treatment Period			Notes/Protocol Section
		Cycle 1		Cycle 2	Subsequent Cycles		EOT	30-Day Follow up	Surviva l Follow up	
Evaluation/Window	Day -28 to -1	Day 1	Day 15	Day 1	Day 1	Day 15	± 7D	± 7D	Q12W ± 7D	
HBV and HCV serology testing and HIV where applicable	X									See Section 7.3.10 and Table 11
LH, FSH and/or estradiol	X									See Appendix 1
Dermatologic examination	X	X			X		X	X		Performed Q8W after C3D1. See Section 7.3.4
Physical exam	X	X		X	X			X		Height to be measured at Screening only; see Section 7.3.3
Vital signs	X	X	X	X	X		X	X		See Section 7.3.5
ECOG / Karnofsky status	X	X		X	X			X		See Section 7.2.5
Full ophthalmic examination	X	Only if clinically indicated								See Section 7.3.12
Triplicate 12-Lead ECG	X	X								Triplicate 12-lead ECGs performed pre-dose on C1D1. See Section 7.3.6 and Table 10 for timing of ECG collection.
Single 12-Lead ECG		X		X	X		X			See Section 7.3.6 and Table 10 for timing of ECG collection
ECHO/MUGA	X			X	Every 12 weeks		X	X		ECHO/MUGA scans will be performed on C2D1, then every 12 weeks. ECHO/MUGA scans should be every 24 weeks (or more frequently if clinical indicated) for patients who have been on treatment for ≥ 24 months without decreases of > 10% in LVEF compared

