Table 3. Schedule of Activities

Procedure/Assessment (± 3-day window for all Treatment Period visits except for CID1 [no window])	Screening	Treatment Period					Post-treatment Period			Notes/Protocol Section
		Cycle 1		Cycle 2	Subsequent Cycles		EOT	30-Day Follow up	Survival Follow up	
Evaluation/Window	Day -28 to -1	Day 1	Day 15	Day 1	Day 1	Day 15	± 7D	± 7D	Q12W ± 7D	
										to baseline and LVEF < LLN at any time while on study. See Section 7.3.11
MRI of brain (and spinal cord at Screening only). Contrast-enhanced CT or MRI of chest, abdomen and pelvis Brain metastasis target and non-target lesion assessment	X			X	At Cycle 2 Day 1, Cycle 3 Day 1 and then every 8 weeks through Cycle 11. After Cycle 11, scans occur every 12 weeks, unless response confirmation. Complete response/partial response confirmation assessments must take place at least 4 weeks after the initial response.					EOT scan NOT required if scan was done within 8 weeks of treatment discontinuation and progressive disease has been documented. See Section 7.2.1
Extracranial target and non-target lesion assessment	X			X	At Cycle 2 Day 1, Cycle 3 Day 1 and then every 8 weeks through Cycle 11. After Cycle 11, scans occur every 12 weeks, unless response confirmation. Complete response/partial response confirmation assessments must take place at least 4 weeks after the initial response.					EOT scan NOT required if scan was done within 8 weeks of treatment discontinuation and progressive disease has been documented. See Section 7.2.1
Dispense encorafenib + binimetinib (with dosing diary)		X		X	X					See Section 6.1 and 6.2
Administer encorafenib + binimetinib		X								Administer daily in 28-day cycles. See Section 6.1
Review dosing diary. Assess encorafenib			X	X	X	X	X			See Section 6.4

Table 3. Schedule of Activities

Procedure/Assessment (± 3-day window for all Treatment Period visits except for CID1 [no window])	Screening	Treatment Period					Post-treatment Period			Notes/Protocol Section	
		Cycle 1		Cycle 2	Subsequent Cycles		EOT	30-Day Follow up	Surviva l Follow up		
Evaluation/Window	Day -28 to -1	Day 1	Day 15	Day 1	Day 1	Day 15	± 7D	± 7D	Q12W ± 7D		
and binimetinib compliance											
Prior/concomitant medication	X	Assess continuously								See Section 6.5	
Adverse event assessment	X	Assess continuously								See Section 7.4	
Document subsequent anticancer therapies								X	X	See Section 7.2.4.2 and 7.2.4.3	
Survival status								X	X	See Section 7.2.4.3	

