4. STUDY DESIGN

4.1. Overall Design

This is a multicenter, randomized open-label Phase 2 study to assess the safety, efficacy and PK of 2 dosing regimens of encorafenib + binimetinib combination therapy in patients with *BRAFV600*-mutant melanoma with asymptomatic brain metastasis. Approximately 110 eligible patients will be enrolled, including 9 patients in a single-arm Safety Lead-in. After a Screening Period, treatment will be administered in 28-day cycles and will continue until disease progression, unacceptable toxicity, withdrawal of consent, start of subsequent anticancer therapy, death. Once the patient discontinues study treatment, the Treatment Period will end, and the patient will enter the Follow-up Period. The 2 doses of encorafenib + binimetinib combination treatment to be evaluated are summarized in Table 5.

The first 9 evaluable patients in the high-dose treatment will constitute the high-dose Safety Lead-in cohort. Evaluable patients for the Safety Lead-in cohort must have experienced:

- either a DLT (Table 7) or
- received at least 75% of the planned cumulative dose of both study drugs during Cycle 1.

If the high-dose treatment is found safe during the Safety Lead-in, based on predefined evaluation criteria (Section 6.6), eligible patients will be randomized (1:1; approximately 50 patients in each treatment arm) to the standard-dose (Arm A) or high-dose (Arm B) treatment arm stratified by:

- baseline number of brain metastases (1 to 2 brain lesions vs. ≥ 3 brain lesions at baseline assessment) and
- history of prior local therapy [e.g., SRS or SRT (yes vs. no)].

Table 5. Planned Treatment Arms

Treatment Arm	Encorafenib Dose	Binimetinib Dose
A (standard-dose) ¹	450 mg QD	45 mg BID
B (high-dose)	300 mg BID	45 mg BID

1. The standard dose arm (Arm A) includes patients who have intra-patient dose escalation (see Section 6.7.2).

If the high-dose treatment is determined not to be safe in the Safety Lead-in, no patients will be enrolled into Arm B, and up to 100 patients will be enrolled into 2 cohorts in the standard-dose Arm A:

- **Cohort 1:** Up to 50 patients with *BRAFV600* cutaneous melanoma with metastases to the brain confirmed by MRI, asymptomatic, and with prior local therapy (e.g., SRS or SRT).

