6.1. Primary Endpoints

6.1.1. Safety Lead-in

The number and proportion of patients experiencing DLTs during Cycle 1 will be summarized by SOC and PT based on maximum toxicity grade. Analyses of DLT will be performed on Dose-determining Set.

All DLTs and their attributes will be presented in data listings sorted by patient identifier, AE and date of onset of the AE.

6.1.2. Phase 2

Main Analysis:

BMRR will be calculated by dividing the number of patients with a BOR of confirmed CR or confirmed PR in brain metastasis by the number of patients in the Efficacy Set in the respective cohort. The corresponding exact Clopper-Pearson 2-sided 90% CI and 95% CI will be calculated.

BOR is defined as the best response recorded from date of the first dose of study treatment until progression by Investigator assessment at each time point. Only tumor assessments performed before the start of any subsequent anticancer therapies will be considered in the assessment of BOR. Clinical deterioration or clinical progression noted on the End of Study completion eCRF will not be considered as documented disease progression. BOR will be determined according to the following rules:

- CR = at least two determinations of CR at least 4 weeks apart and documented before progression and start of new anticancer therapy.
- PR = at least two determinations of PR or better (and not qualifying for a CR) at least 4 weeks apart and documented before progression and start of new anticancer therapy.
- SD (for patients with at least one measurable lesion at baseline)= at least one SD assessment (or better and not qualifying for CR or PR) ≥ 6 weeks after date of the first dose and before progression and start of new anticancer.
- Non-CR/Non-PD (for patients with only non-target disease at baseline) = at least one Non-CR/Non-PD assessment (or better and not qualifying for CR or PR) ≥ 6 weeks after date of the first dose and before progression and the start of new anticancer therapy.
- PD = progression ≤ 16 weeks after date of the first dose (and not qualifying for CR, PR or SD).
- Not Evaluable (NE) = all other cases.

The frequency (number and percentage) of patients with BOR in brain metastasis of CR, PR, SD, PD, non-CR/non-PD (applicable only to patients with non-measurable disease at baseline), and NE will be tabulated.

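### An in-window Cycle 3 Day 1 scan can fall under 28 days after a Cycle 2 Day 1 response and be unable to confirm it; this mostly delays confirmation but can lose a few responses

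*Protocol*

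**What the plan says.** - **Scan times.** The Schedule of Activities (Protocol Table 3) places brain and extracranial scans "At Cycle 2 Day 1, Cycle 3 Day 1 and then every 8 weeks through Cycle 11". Protocol Section 4.1 says "treatment will be administered in 28-day cycles", so C2D1 and C3D1 are 28 days apart on paper and the next scan is at Cycle 5 Day 1 (C5D1).
- **Windows.** The Table 3 header gives a plus-or-minus "3-day window for all Treatment Period visits except for C1D1 [no window"]. Section 7.2.1 says of imaging: "Post-Screening assessments will be performed as described in the SoA (Table 3) (± 7 days"). SAP Table 3 (Section 6.2.4) also carries a ±3-day window.
- **Confirmation in the protocol.** Section 7.2.1 says "Confirmation assessments must be performed no less than 4 weeks after the criteria for response have initially been met", and allows the next scheduled assessment to serve. The same paragraph provides for a confirmation scan ahead of the next scheduled one and lets a PR be confirmed later than the next assessment. Table 3 repeats the 4-week minimum.
- **Confirmation in the SAP.** Section 6.1.2 defines "PR = at least two determinations of PR or better (and not qualifying for a CR) at least 4 weeks apart", before progression and new anticancer therapy, with a parallel rule for CR. The two scans need not be consecutive. Section 5.2.7 counts unscheduled tumor assessments.
- **Use.** The primary analysis is based on confirmed responses (Protocol Section 8.4.1). It waits until initial brain responders have at least 6 months of follow-up (SAP Section 6).

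**The concern.** For a response first seen at C2D1, the nominal gap to the next scan equals the confirmation minimum with no margin, and both windows allow shorter gaps. A site can obey the visit schedule fully and still produce a second scan that shows response but cannot count as confirmation. Nothing tells the site to check the interval, and Section 7.2.1 itself offers the next scheduled assessment as the place to confirm.

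If such a patient then progresses by C5D1, the primary analysis records a non-responder although response was seen on two scans. The rationale for the trial stresses that intracranial responses are short, so this is not a negligible possibility. The stake is a small downward shift in confirmed BMRR, and in power, caused by visit timing and not by the drug.

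**Working it through.** **1. The plan's own figure.** Protocol Section 8.2 rejects BMRR ≤ 30% with at least 21 responses in 50 and states about 90% power at 50%, one-sided 5%. Exact binomial: P(X ≥ 21 | 50, 0.30) = 0.0478 and P(X ≥ 21 | 50, 0.50) = 0.8987. The figure reproduces.

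**2. Possible gaps.** With deviations *a* and *b* (whole days, each within ±w), gap = nominal + *b* − *a*.

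| Pair | Nominal | w = 3 | w = 7 |
|---|---|---|---|
| C2D1 to C3D1 | 28 d | 22 to 34 d | 14 to 42 d |
| C3D1 to C5D1 | 56 d | 50 to 62 d | 42 to 70 d |
| C2D1 to C5D1 | 84 d | 78 to 90 d | 70 to 98 d |

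Only the first pair can fall under 28 days. A response first seen at C3D1 is unaffected, and a C2D1 response that persists is always confirmable at C5D1.

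**3. How often the first pair is short.** If deviations were independent and uniform (an assumption), 21 of 49 pairs (42.9%) are under 28 days with ±3, and 105 of 225 (46.7%) with ±7.

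**4. Chance that a delay becomes a loss.** As an illustration, take an exponential duration with median 6.5 months, the figure Protocol Section 2.1.3 cites for another BRAF/MEK combination in brain metastases. With λ = ln 2 / 6.5 = 0.1066 per month and 30.4375 days per month (SAP Section 5.2.11), the chance of still responding 28 days after C2D1 but having an event by day 84 is

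exp(−λ·28/30.4375) − exp(−λ·84/30.4375) = 0.907 − 0.745 = 0.162.

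**5. Effect on rate and power.** Fraction lost = share first responding at C2D1 × share of short gaps × 0.162. This assumes no off-schedule scans and takes 50% as the rate before the loss.

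| C2D1 share | Short gaps | Fraction lost | BMRR | Power |
|---|---|---|---|---|
| 40% | 20% | 0.013 | 0.4935 | 0.881 |
| 80% | 45% | 0.058 | 0.4709 | 0.806 |
| 25% | 42.9% | 0.017 | 0.4913 | 0.875 |
| 100% | 46.7% | 0.075 | 0.4623 | 0.770 |

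The first two rows are the working range. The last two show how far the result moves when the assumed shares change. If off-schedule confirmation scans are done, the fraction lost is about zero and power stays near 0.90.

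**6. Whether a one-sided window around nominal C3D1 would do.** With C3D1 at 0 to +7 of its nominal date and C2D1 at ±7, 28 of 120 day-pairs (23%) are still under 28 days. With C2D1 at ±3, it is 6 of 56 (11%). Only anchoring to the actual C2D1 scan date removes short gaps.

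**The case against.** The strongest reply is that the documents already handle most of this. The 4-week minimum is a requirement in Section 7.2.1 and again in Table 3, so a site with a C2D1 responder can book the C3D1 scan late in its window or add an unscheduled scan. The SAP accepts any two qualifying scans and counts unscheduled ones. The wait for 6 months of follow-up means the analysis cut-off does not remove the C5D1 scan. Confirmed plus unconfirmed BMRR is a prespecified supportive estimand (SAP Section 2.1.2), so these patients are visible there. Any loss makes rejecting the null harder and cannot create a false positive.

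All of that stands, and it rules out a stronger inference that a reader might draw: that early responses go unconfirmed through scheduling alone, or that the 43% to 47% of short gaps translate into a similar loss of early responses. A short gap by itself costs nothing if the response lasts to C5D1.

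The size is also open to challenge. Neither the C2D1 share nor the short-gap share comes from the documents. The 50% alternative could be read as already being the confirmed rate, in which case subtracting from it counts the loss twice.

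What the reply does not remove: the off-schedule scan is optional, and no text ties the C3D1 date to the actual C2D1 date. The protocol's later-confirmation sentence names PR only, although the SAP rule covers CR too. Protocol Appendix 5 counts only scans before new therapy and within 30 days of the last dose, a limit SAP Section 6.1.2 does not repeat. Stopping treatment can therefore also use up eligible scans, though an end-of-treatment scan may partly cover that route.

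**Conclusion.** The point holds as a modest, avoidable weakness in scheduling. The C3D1 scan can be in window and still too early to confirm a C2D1 response, and the two stated windows disagree. Four things must coincide for a response to be lost: first response at C2D1; a gap under 28 days; no off-schedule scan; and progression, death, new therapy or no further eligible scan before a later one confirms.

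Under an exponential duration with median 6.5 months, 40% to 80% of responses starting at C2D1, 20% to 45% short gaps, no off-schedule scans, and 50% taken as the rate before this loss, BMRR falls to between 49.4% and 47.1% and power from about 0.90 to between 0.88 and 0.81. These are illustrations, not estimates. The direction is against the drug, and type I error is not inflated. The documents do not support saying that the plan makes early responses unconfirmable.

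**What to change.** - Keep the 4-week rule. When the C2D1 scan shows CR or PR, book the C3D1 scan 28 to 35 days after the actual date of the C2D1 scan, not at 0 to +7 days around nominal C3D1. State that a C3D1 scan moved for this reason is not a deviation.
- State one imaging window in the Schedule of Activities and Section 7.2.1, and align the window in SAP Table 3 with it.
- In the SAP, add a count of responses seen on two scans under 28 days apart that were never confirmed.

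The cost is schedule wording, a site memo and one extra table line. No scan is added, and the decision rule and alpha do not change. The downside is slightly less scheduling flexibility for early responders, and some C3D1 scans will fall later than the nominal window. For example, a C2D1 scan done at +7 days puts the C3D1 scan at +7 to +14 days.
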